Detection of livery injury by radiation was first demonstrated in the late 1960's using 2-dimensional planar scintigraphy [27-29]. The inability to obtain 3-dimenstional spatial assessment of SC distribution in the liver and spleen hampered the routine use of SC in the clinic as well as application into the radiation and surgical oncology fields. Recently, the development of SPECT/CT technology has allowed improved regional contrast resolution relative to planar scintigraphy between functional, dysfunctional and non-functional liver from tomographic image acquisition, along with increased accuracy in local SC activity estimation from CT-based attenuation correction [30, 31]. Modern SC SPECT/CT imaging techniques, therefore, provide the potential for volumetric and spatial characterization of liver function prior to and in response to therapy. Preliminary retrospective data from our group have shown that measuring "total liver function" (derived from the product of functional liver volume and liver-to-spleen mean uptake) on pre-treatment SC SPECT/CT in 30 HCC patients may improve risk stratification and outcome prediction [32]. These data need to be validated prospectively with standardization of imaging protocols. Furthermore, changes in global or regional liver function as assessed with SC SPECT/CT, however, have not been studied in the context of RT and surgical resection of the liver.

Risks/Benefits

The primary risk to patients in this study is the risk associated with the two additional SPECT/CT ^{99m}Tc-SC scans. The radiation treatments or surgery that patients receive will be standard of care. Risks associated with the two SPECT/CT ^{99m}Tc-SC scans include: patient time (approximately 1 hour per scan); radiation dose from radioactive tracers and CT scans (up to ~ 30 mSv per session, which is about 0.1% of the usual radiation dose for liver cancer treatment, typically around 60 Gy), and intravenous injection and associated potential for bleeding, pain, infection, and injection site reaction.

In patients who opt to undergo the indocyanine green clearance study, there is the risk of art additional intravenous access procedure for the injection of the indocyanine green dye (injection of the indocyanine green must be separate from the intravenous access of the blood draw). Please see consent form for further details on potential risks.

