3.0 STUDY OBJECTIVES

3.1 Primary Objectives

- a) Develop new quantitative metrics of baseline SC uptake on SPECT/CT imaging and correlate with clinical parameters of liver function and clinical outcomes in liver cancer patients receiving RT or surgery.
 - Hypothesis: Global metrics of baseline pre-treatment SC uptake on SPECT/CT imaging are more predictive for survival than conventional clinical measures of liver function and are associated with ICG clearance. For patients receiving surgery, the volume of the future liver remnant (FLR) as defined by SC SPECT/CT imaging (functional FLR) is more predictive for PHLF than CT-defined FLR volumes. Heterogeneity metrics of baseline SC uptake are associated with the severity of cirrhosis and prior liver-directed therapy; specifically, SC uptake within the liver is more heterogeneous in less compensated livers and in those that have received a higher number of liver-directed therapies.
- b) Correlate *post-treatment* changes in SC uptake on SPECT/CT imaging with changes clinical liver function.

Hypothesis: Changes in SC uptake between pre-RT and mid-RT/post-RT SPECT/CT scans are associated with changes in clinical liver function in response to RT and are predictive of liver toxicity at earlier time points compared to clinical assessments of liver function. SC uptake in the FLR (non-treated) is stable and preserved over time between pre-surgery and immediately post-surgery (3-5 days postoperative) scans.

Secondary Objectives

- a) Estimate the dose response relationship on multiple spatial scales (global liver, regional liver, liver image voxel) between radiation dose and changes in SC uptake, both acutely (mid-RT) and subacutely (1 month post-RT), using SC SPECT/CT imaging.
 - Hypothesis: Deficits in SC uptake due to absorbed dose is governed by a linear dose relationship. As the dose delivered to the region/voxel increases, the uptake in SC decreases in a linear fashion.
- b) Estimate the degree of radiation response in liver tissue with varying levels of function (i.e. compare radiation dose response of well compensated livers against less compensated livers).

This may establish a threshold of liver tissue that would be "safe" to treat without significantly affecting liver function.

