4.1.1 Primary Endpoints

a) In this study, patients with liver cancer will undergo SPECT/CT imaging with ^{99m}Tc-SC at the time of RT planning for cohort A and within 1-2 weeks prior to surgery for cohort B. All image datasets will be imported into MIM 6.0, and fused with the RT planning CT and radiation plan for cohort A and with the contrast-enhanced diagnostic CT or MRI scan.

To characterize whole-organ liver function, all pre-treatment SPECT/CT images will be analyzed for 1) ratios of maximum, mean, and total liver SC uptake relative to spleen SC uptake (L/S) and 2) volumetric SC parameters such as the functional liver volume (FLV) formed by 58% maximum image intensity threshold segmentation. Optimal image thresholds for SC SPECT parameter association to CTP classification (A vs. B/C class) will be interrogated by receiver-operator characteristic (ROC) analysis. Image thresholds that yield maximum AUC in quantitative parameters such as FLV ratio, L/S ratio, and their total liver function (TLF) product will be propagated to the remaining analyses. In cohort A receiving RT, planned dose-volume and dose-function metrics within the tumor-subtracted liver and functional liver volume(s) will

feature mean dose, $D_{xx\%}$ (the dose given to xx% of liver volume), V_{zz} (the liver volume which receives zz Gy), and fV_{zz} (the percentage of total liver function which receives zz Gy).

To characterize spatial distribution of functional liver, radiomics will be applied to SC SPECT/CT images via a locally-developed open source radiomics toolkit [33]. In addition to the whole-organ SC SPECT/CT metrics descried above, radiomic features will include intensity histogram features, along with a variety of textural features derived from co-occurrence matrices, neighborhood difference matrices, and zone size matrices [34-36].

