As a validation step, these baseline SC imaging data will be correlated to indocyanine green (ICG) clearance in patients (in those who opt to undergo this study), which assesses liver function based on the rate of clearance of a contrast agent over serial blood draws, and is considered a standard assessment of global liver function. ICG is a water-soluble compound that is selectively taken up by hepatocytes and transported into the biliary system without undergoing metabolism [37]. ICG clearance, therefore, can be utilized as an index of functioning hepatocyte mass [38] and is correlated with prediction of liver dysfunction and mortality associated with surgical resection [39]. The retention rate of ICG 15 minutes after administration (ICG-R15), a ratio of the ICG concentration at 15 minutes to its initial concentration in the blood, will be used to benchmark SC uptake metrics against. Higher ICG-R15 rates indicate worse liver function and would be expected to be correlated with lower global SC uptake metrics.

Functional FLR will be generated by calculating the volume of liver within the optimal image threshold as defined above. Anatomic FLR will be delineated and calculated on CT or MRI images using portal and hepatic veins as landmarks for segmental division. Logistic regression analyses and Pearson chi-square test will be used to compare the ability to predict for PHLR between functional FLR and anatomic FLR.

b) Correlate *post-treatment* changes in SC uptake on SPECT/CT imaging with changes clinical liver function. Relative changes in the parameters identified at baseline will be tested for correlation to changes in clinical liver function, including CTP score and ALBI grade, as well as their individual constituents.

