4.2.1 Primary Endpoints

a) Significant differences in Wilcoxon rank sum of ROC-optimized SC SPECT parameters will be tested between CTP classes. Spearman rank correlations between optimal SC SPECT parameters and clinical liver function parameters will be tabulated for the following categories: (1) composite liver function scoring systems (CTP score, ALBI grade), (2) individual quantitative liver function components (albumin, bilirubin, INR), and (3) individual qualitative clinical liver function components (encephalopathy, portal hypertension, ascites, and splenomegaly). Qualitative components will be treated as binary categorical variables (yes/no). Imaging and clinical parameters of liver function will be tested for association with overall survival. Continuous variables will be dichotomized above and below a threshold value that maximized accuracy of classification under ROC with balanced sensitivity and specificity. Univariate Cox proportional hazard regression will then be performed on all continuous and categorical variables. Statistically significant variables will serve as inputs into multivariate Cox proportional hazard regression. A stepwise backwards variable selection procedure will be followed to remove non-significant variables with high cross-correlation until the model log-likelihood is maximized.

Because radiomics generates feature sets of ~50 metrics, machine learning methods will be utilized to develop predictive models that are robust against overfitting, utilizing feature selection and classification/regression methods such as support vector machines, Bayesian analysis, and decision trees. These machine learning methods will be compared against standard statistical methods, such as ROC analysis and Kaplan-Meier estimation / Cox regression, for association to clinical liver function, prior liver-directed therapies, clinical outcomes (i.e. survival), and toxicity (i.e. CTP score progression).

b) The same set of statistical analysis will be performed for association of post-treatment changes in SC uptake on SPECT/CT imaging to clinical endpoints. Machine learning methods will test whether post-treatment changes in SC SPECT/CT provide independently predictive information after adjusting for baseline parameters.

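### Section 4.2.1, survival: the backward-selection stopping rule conflicts with its removal rule, and no planned analysis formally compares SC with clinical measures as predictors of survival

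*Combined protocol and SAP*

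**What the plan says.** Section 4.2.1, item a, opens the survival analysis with the statement that "Imaging and clinical parameters of liver function will be tested for association with overall survival". Continuous variables are first split at a threshold chosen by ROC, and univariate Cox models follow. Then "Statistically significant variables will serve as inputs into multivariate Cox proportional hazard regression", and a backward procedure is used to "remove non-significant variables with high cross-correlation until the model log-likelihood is maximized". No significance level is given for the screen or the removal, no cut-off for cross-correlation, and no penalised criterion.

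The hypothesis under primary objective a (Section 3.1) is comparative: global baseline SC metrics "are more predictive for survival than conventional clinical measures of liver function". For the future liver remnant (FLR), Section 4.1.1 does name a matching comparison, using logistic regression and a chi-square test to "compare the ability to predict for PHLR between functional FLR and anatomic FLR". The survival text has no counterpart.

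Two further statements matter for the fix. Section 2.0 describes total liver function (TLF) as "derived from the product of functional liver volume and liver-to-spleen mean uptake". Section 4.1.1 names a functional liver volume "formed by 58% maximum image intensity threshold segmentation", but also says that the threshold with the largest AUC for Child-Turcotte-Pugh (CTP) class in volume, liver-to-spleen ratio and their "product will be propagated to the remaining analyses".

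**The concern.** The selection sentence gives an action and a stop that pull in opposite directions. An analyst who obeys the stop keeps everything that passed the univariate screen. One who obeys the action may drop some of it. The reported hazard ratios would then depend on a choice that the plan does not record.

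The second issue is that a comparative primary hypothesis is left to be answered by default. If an SC metric stays in the final model and CTP score drops out, it is natural to report that SC predicts survival better. Elimination among correlated predictors cannot carry that conclusion.

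**Working it through.** The plan gives no expected deaths, effect sizes, correlations or significance level for survival, so there is no figure of its own to reproduce. Step 1 is mathematical. Steps 2 and 3 are simulations in which only n = 60 (40 radiation plus 20 surgery, Section 4.0) comes from the documents. Step 4 is a reading of the text.

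**1. Can removing a variable raise the log-likelihood?** Let l(β) be the Cox partial log-likelihood for the larger model. Deleting variable j fixes β_j = 0, so

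max l(β) subject to β_j = 0 ≤ max l(β).

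The maximum is therefore always at the starting model. High cross-correlation does not alter this. As a check, three simulations found 0 increases in 4,500, 8,556 and 5,559 single deletions (4,500 + 8,556 + 5,559 = 18,615).

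A penalised criterion behaves differently. With AIC = −2l + 2k, deleting one variable changes AIC by 2 × (fall in l) − 2, so AIC accepts the deletion when the fall is below 1. In the 4,500-deletion set (five candidates, pairwise correlation 0.6), the median falls were 0.31, 0.38 and 0.49 at 9, 18 and 36 deaths:

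- 9 deaths: 2 × 0.31 − 2 = −1.38
- 18 deaths: 2 × 0.38 − 2 = −1.24
- 36 deaths: 2 × 0.49 − 2 = −1.02

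AIC would accept the typical deletion; the written stop would accept none.

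**2. How often do the two clauses end in different models?** Assumed: five continuous candidates, log hazard ratios 0.6, 0.4, 0, 0, 0 per SD, and a univariate screen at p<0.05. The removal clause is taken as written, so a variable goes only if it has p>0.05 and also exceeds a correlation cut-off with another variable. The cut-off is not in the plan, so three were tried (400 runs per setting). The last column drops the correlation condition (500 runs).

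| Deaths, correlation | Cut-off 0.5 | Cut-off 0.7 | Cut-off 0.8 | No condition |
|---|---|---|---|---|
| 18, 0.5 | 67% | 2% | 0% | 80% |
| 26, 0.5 | 78% | 7% | 0% | 92% |
| 35, 0.5 | 85% | 6% | 0% | 95% |
| 26, 0.3 | 14% | 0% | 0% | 68% |
| 26, 0.7 | 97% | 88% | 22% | 98% |

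A repeat over the same settings gave 13–97%, 0–87% and 0–21% for the three cut-offs, and 63–97% without the condition. As the sentence is written, the range is about 0% to 97%.

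**3. Does retention show which variable predicts better?** Assumed: one SC and one clinical variable, equally prognostic (log hazard ratio 0.4 per SD each), correlation 0.6, screen at p<0.05, then removal at p>0.05, 1,000 runs.

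| Deaths | SC alone | Clinical alone | Both | Neither |
|---|---|---|---|---|
| 9 | 28% | 31% | 0.3% | 41% |
| 18 | 41% | 42% | 3% | 14% |
| 36 | 42% | 44% | 13% | 2% |

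With correlation 0.5 to 0.7 and 18 to 35 deaths, SC stays alone in 38–46% of studies and the clinical variable alone in 39–46%. So when only one remains, that fact does not show it to be the better predictor.

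**4. Is a comparison planned elsewhere?** The synopsis lists Kaplan-Meier, log rank and Cox methods, and cross-validated prediction models, with no SC-versus-clinical contrast. The machine-learning text in Section 4.2.1 sets one class of method against another, not SC against clinical predictors. Item b tests whether post-treatment SC changes add to baseline parameters, which is a different question. Only the FLR comparison is explicit, and it concerns liver failure after surgery.

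**The case against.** The best reply is that this is a single-arm pilot and the sentence is merely loose: no analyst told to eliminate variables would keep them all, and a penalised criterion was probably meant. That may be so, but none is named, and AIC, BIC and a p-value rule need not agree. Missing data do not rescue the wording either. ICG clearance is optional, so the patient set can change as variables leave, and log-likelihoods from different patients are not comparable.

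Three stronger readings are tempting, and the documents do not support them.

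- A reader might infer that the two clauses nearly always give different models. Figures of 63–98% arise only if the correlation condition is ignored, and that condition is part of the written rule.
- A reader might infer that nothing in the plan bears on SC against clinical measures for survival. In fact both kinds of variable can enter the same Cox model if they pass the screen, which gives mutually adjusted associations. What is missing is a formal comparison of predictive ability.
- A reader might infer that the procedure favours SC. The one-against-one simulation shows instability, not bias. It does not settle the matter for the plan's larger pool of several SC metrics and about nine clinical variables.

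It also stands that the simulations use continuous covariates and skip the planned ROC dichotomisation, so they illustrate the rule and do not forecast this trial.

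**Conclusion.** Both parts hold. The conflict between stopping and removal is a mathematical fact on a fixed set of patients and needs no assumption. Its practical effect does: about 0% to 97% disagreement, governed mainly by the missing correlation cut-off and by how correlated the candidates are. The absence of a formal SC-versus-clinical comparison for survival follows from reading Sections 1.0, 3.1, 4.1.1 and 4.2.1 together. The coin-toss result assumes two equally prognostic continuous variables.

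Pilot status lowers the precision to be expected. It does not excuse a stop that cannot be followed alongside its own action, or a comparative primary hypothesis without a formal comparison. Both should be corrected before the survival data are analysed.

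**What to change.** (a) Replace the stopping clause with backward elimination by AIC on one fixed set of patients. State the univariate screening level. Label the selected model exploratory.

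(b) For the survival hypothesis, pre-specify TLF at the fixed 58% threshold and CTP score, both undichotomised, in Cox models stratified by cohort (radiation or surgery). The fixed threshold avoids using a TLF tuned to CTP class in the same patients. Report:

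- the likelihood-ratio test of CTP score against CTP score plus TLF, which addresses added value; and
- the bootstrap difference in C-index, TLF alone minus CTP score alone, from within-cohort pairs, with a 95% CI.

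Claim that SC predicts survival better only if that interval lies above zero. Otherwise report a pilot estimate.

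The cost is wording and a little analysis, with no extra scans, visits or patients. The drawback is precision. In an unstratified simulation with two continuous predictors, the 95% half-width was 0.11–0.14 at 18 deaths and 0.08–0.10 at 35. With correlation 0.5:

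| True C-index gain | Deaths | CI above zero | Likelihood-ratio test rejects |
|---|---|---|---|
| 0.10 | 18 | 31% | 84% |
| 0.10 | 35 | 53% | 97% |
| 0.055 | 18 | 14% | 55% |
| 0.055 | 35 | 19% | 85% |

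Superiority will therefore often be inconclusive, and the plan should say so. Intervals would be wider still if survival is captured only to 6 months, the point named for record review and for survival data after withdrawal in Section 7.0, and fewer deaths occur.

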1.0 INTRODUCTION

Title	Functional Liver Imaging with Sulfur Colloid SPECT/CT in Primary and Metastatic Liver Cancer Patients Receiving Liver-Directed Treatment: A Pilot Study
Short Title	Sulfur Colloid SPECT/CT for Liver Cancers
Phase	Pilot Study
Methodology	Single Arm Open-Label
Study Duration	4 years
Study Center(s)	University of Washington Medical Center
Objectives	Study the use of SPECT/CT imaging with ^{99m} Tc sulfur colloid to characterize functional liver in patients receiving liver-directed treatments for liver cancers, and characterize liver tissue response to these treatments. The long-term goal is to use functional liver imaging to personalize liver-directed therapies in liver cancer patients by improving risk stratification and reduce treatment-related hepatotoxicity.
Number of Subjects	60 evaluable subjects
Diagnosis and Main Inclusion Criteria	Patients diagnosed with primary (hepatocellular carcinoma, cholangiocarcinoma) and metastatic liver cancers receiving liver-directed therapies (external beam radiation therapy, surgery).
Study Product, Dose, Route, Regimen	99mTc sulfur colloid SPECT/CT scans
Duration of administration	Drug administration will consist of 3 SPECT/CT scans with ^{99m} Tc sulfur colloid (one baseline scan which is standard of care, two follow-up scans which are experimental and paid for by departmental research funds).
Statistical Methodology	^{99m} Tc sulfur colloid SPECT/CT parameters will be extracted, selected, and tested for statistical association to clinical liver function status and post-treatment toxicity using a variety of statistical methodologies. Receiver-operator characteristic (ROC) analysis will determine the optimal operating point for liver function classification accuracy using SC SPECT/CT parameters. Hypothesis testing of differences between independent groups will proceed using non-parametric Wilcoxon ranksum between 2 groups or Kruskal-Wallis ANOVA between >2 groups. Hypothesis testing of differences between imaging time points of the same subjects will proceed using non-parametric Wilcoxon sign-rank or Friedman ANOVA paired comparison. Survival analysis will consist of Kaplan-Meier estimation, log rank testing, and Cox proportional hazard regression. Dose-response models will be constructed from linear and logistic regression. Prediction models will utilize robust feature selection and feature fitting through multi-fold cross validation as part of a general machine learning framework.

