4.0 STUDY DESIGN

General Design

This is a pilot study of utilizing SPECT/CT imaging with 99m Tc-SC to accurately identify and quantitate functional liver tissue on serial imaging in patients receiving RT or surgery for liver cancer. The long-term goals are to use functional imaging to improve risk stratification for selecting which patients should undergo aggressive local treatments with RT or surgery and to aid in RT planning by preferentially sparing functional liver tissue, thereby leading to reduced liver toxicity. There will be two cohorts of patients: those receiving RT (Cohort A) and those undergoing surgery (Cohort B). A total of 60 patients will be enrolled (Cohort A, n = 40; Cohort B, n = 20).

All patients will have a total of 3 SPECT/CT imaging with ^{99m}Tc-SC. The first scan in both cohorts will be routine medical care (not experimental) and will take place prior to initiation of RT or surgery. Two follow up scans will be part of the protocol. In cohort A, the first follow up scan will occur at mid-RT, and the second one about 1 month post-RT (prior to any potential anatomical liver changes). In cohort B, the first follow-up scan will occur 3-5 days postoperatively (prior to any potential liver hypertrophy), and the second one about 1 month post-operatively (when liver hypertrophy is expected to occur).

Endpoints

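### Cross-validation is stated only for the machine-learning models, so as written the comparison with ROC and Cox results sets held-out against apparent performance and leans towards the standard methods

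*Combined protocol and SAP*

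**What the plan says.** The enrolment target is in section 4.0: "A total of 60 patients will be enrolled (Cohort A, n = 40; Cohort B, n = 20").

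**Machine-learning side.** The Statistical Methodology row of the Introduction states: "Prediction models will utilize robust feature selection and feature fitting through multi-fold cross validation as part of a general machine learning framework". Section 4.2.1(a) gives the reason for this route, "Because radiomics generates feature sets of ~50 metrics", and its aim: "machine learning methods will be utilized to develop predictive models that are robust against overfitting". The number of folds, any repeats, and which steps are nested inside the folds are not given.

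**Standard side.** Section 4.1.1(a) picks the image threshold with the highest AUC for CTP class A versus B/C and carries it into everything that follows. Section 4.2.1(a) then says: "Continuous variables will be dichotomized above and below a threshold value that maximized accuracy of classification under ROC with balanced sensitivity and specificity". Variables that are significant in univariate Cox regression go into a multivariate Cox model, which is reduced by backward selection. No split, cross-validation, bootstrap or optimism correction is mentioned for any of these steps.

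**The comparison.** Section 4.2.1(a): "These machine learning methods will be compared against standard statistical methods, such as ROC analysis and Kaplan-Meier estimation / Cox regression", for clinical liver function, prior therapy, survival and toxicity. No performance measure and no common validation scheme is named. Item (b) repeats the same analyses for post-treatment changes and adds: "Machine learning methods will test whether post-treatment changes in SC SPECT/CT provide independently predictive information after adjusting for baseline parameters".

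**The concern.** A performance figure computed on the patients who supplied the cut-point, the screen and the selected variables is optimistic. A cross-validated figure largely is not. Setting one against the other gives the side without cross-validation a head start unrelated to how well it would predict in new patients.

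The plan chooses machine learning for its protection against overfitting, yet describes no such protection for the comparator. At stake is the pilot's answer to whether radiomics and machine learning add anything to ROC and Cox methods. That answer would feed the long-term aim of risk stratification in section 4.0. The error runs one way: it can hide a real machine-learning advantage, and it can inflate the margin of a standard method that is truly better.

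**Working it through.** The documents give no event count, power or effect size, so there is no planned figure to reproduce. Inputs from the documents: N = 60 (40 in Cohort A, 20 in Cohort B) and about 50 radiomic features. Assumed: event counts, numbers of candidate variables, independent features, and a 0.05 level for the Cox screen. Section 7.0 has a record review at 6 months but gives no expected number of deaths.

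**1. Best marker, pure noise, by formula.** For one uninformative marker with n1 events and n0 non-events, the AUC has mean 0.5 and

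SD = √[(n1 + n0 + 1) / (12 · n1 · n0)].

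With n1 = 15 and n0 = 45: √(61 / 8100) = 0.0868. Choosing the best of k independent markers, in either direction, gives an expected apparent AUC of about 0.5 + SD × E(max |Z| over k). The expected maxima are 0.798, 1.57 and 2.51 for k = 1, 5 and 50:

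- k = 1: 0.5 + 0.0868 × 0.798 = 0.57
- k = 5: 0.5 + 0.0868 × 1.57 = 0.64
- k = 50: 0.5 + 0.0868 × 2.51 = 0.72

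The true AUC is 0.50 throughout.

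**2. Best marker, by simulation.** Optimism = apparent AUC − AUC with the choice of marker repeated inside each of 5 stratified folds (n = 60, 15 events).

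| Setting | Apparent | Held-out | Gap |
|---|---|---|---|
| 50 noise features | 0.72 | 0.51 | 0.21 |
| 5 noise features | 0.63 | 0.49 | 0.14 |
| 5 features, one with true AUC 0.70 | 0.71 | 0.64 | about 0.07 |
| 5 features, one with true AUC 0.75 | 0.76 | 0.73 | about 0.03 |
| 5 features, one with true AUC 0.80 | 0.80 | 0.79 | about 0.02 before rounding |

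A separate rerun of these settings gave gaps of 0.22, 0.14, 0.07, 0.04 and 0.02. Five correlated informative metrics (assumed correlation 0.7, true AUC 0.70 to 0.75) gave gaps of about 0.05. In smaller sets the null optimism grows: with 50 noise features, apparent 0.76 against 0.49 for 40 patients with 10 events, and 0.86 against 0.50 for 20 patients with 5 events.

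**3. Planned Cox route, null survival data.** ROC cut-point, univariate screen, backward selection; 60 replicates per setting.

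| N / deaths | Candidates | Apparent C | 5-fold C | C in new patients |
|---|---|---|---|---|
| 60 / 18 | 6 | 0.65 | 0.51 | 0.50 |
| 60 / 18 | 12 | 0.72 | 0.48 | 0.50 |
| 60 / 30 | 6 | 0.62 | 0.49 | 0.49 |
| 60 / 30 | 12 | 0.67 | 0.49 | 0.50 |
| 40 / 16 | 6 | 0.66 | 0.51 | 0.51 |
| 40 / 16 | 12 | 0.71 | 0.50 | 0.50 |

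At least one variable passed the screen in 90 to 100% of these null trials. Some Cox fits gave convergence warnings, so these figures are approximate.

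**4. Can the winner change?** Best single marker against a ridge linear classifier standing in for a linear support vector machine; N = 40 or 60; 12 or 50 features; signal spread over half of them; truth taken from 2,000 new patients. With the standard side scored on its own training data and machine learning by 4-fold cross-validation, the truly worse method was named the winner in 71 to 88% of trials. With both sides cross-validated it was 31 to 41%. In these scenarios machine learning was truly better in 83 to 97% of trials, so they show what the bias can do, not how often it would matter here.

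**The case against.** **The premise rests on silence.** A reader might infer that the plan states the ROC and Cox models are fitted and scored on all patients. It does not. The Introduction's sentence begins with prediction models in general and could be stretched to cover a predictive Cox model. That stands as a limit on the wording. But the same sentence places cross-validation in a machine-learning framework, and section 4.2.1 never extends it to ROC or Cox.

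**The large null gaps are a worst case.** The roughly 50 radiomic features are sent to machine learning because there are so many; the Cox route is described for imaging and clinical measures of liver function, probably a smaller set. The Background also cites preliminary data suggesting that total liver function is informative. This stands: with real signal in a few metrics, marker-selection optimism is small, although stepwise Cox adds more. A reader might go further and call any conclusion from the comparison an artefact, or the optimism as large as any plausible true difference. The documents state no plausible difference, and the bias cannot reverse the ranking when the standard method is truly better.

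**Item (b).** A reader might infer that the named machine-learning methods cannot test for independent information at all. The list is open and includes Bayesian analysis, and item (b) also applies the same analyses as item (a), including multivariate Cox regression, which gives adjusted effects. That criticism is not supported.

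**It is a pilot.** No stated hypothesis concerns machine learning versus standard methods, and no treatment decision depends on it. True, but the comparison sits under the primary endpoints and equal footing costs little.

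**Conclusion.** The point holds as a defect of specification with a known direction. Followed as written, the comparison favours the standard methods. A machine-learning win would be conservative, provided all its own tuning sits inside the folds. For the CTP endpoint that includes the image threshold, which is tuned to CTP class upstream of both sides. A standard-method win could not be relied on.

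The size is not fixed by the documents. Under the assumptions above (60 patients, 15 events), it runs from about 0.02 to 0.07 AUC when one of five metrics is truly informative, to 0.14 (5 candidates) and 0.21 (50 candidates) on pure noise. The stepwise Cox route gives a null apparent C of 0.65 to 0.72 against about 0.50 with 18 deaths. A single prespecified marker carries less (apparent 0.57 on noise). Equal footing removes the bias but not the imprecision, as the remaining 31 to 41% of wrong winners show. The change should be made, but the study does not fail without it.

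**What to change.** In section 4.2.1, state one validation scheme for both pipelines:

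- Use the same repeated folds, stratified by event, for machine learning and for ROC/Cox. Inside each training fold redo the image threshold, cut-point, screening, variable selection and tuning. Bootstrap optimism correction applied to both sides is an acceptable alternative.
- Name one measure per endpoint: AUC for binary outcomes, c-index for survival.
- Report the paired difference in held-out performance with an interval, and label it exploratory.
- Optionally, for item (b), report held-out performance of baseline-only against baseline-plus-change models on the same folds.

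If cross-validation was already meant for both sides, one sentence saying so settles the main point. The cost is analysis code only, with no extra patients, scans or visits. Reported performance of the standard methods will be lower.
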